4.11.2 Adverse Events of Special Interest (AESI)

The following conditions should be considered AEs of special interest:

- a. ALT or AST $\geq 8 \times$ ULN
- b. ALT or AST $\geq 5 \times$ ULN for 2 or more weeks
- c. ALT or AST $\geq 3 \times$ ULN **and** total bilirubin $\geq 2 \times$ ULN (or ALT or AST $\geq 3 \times$ ULN **and** INR > 1.5)
- d. ALT or AST $\geq 3 \times$ ULN accompanied by clinical symptoms believed to be related to hepatitis or hypersensitivity, such as new or worsening of fatigue, nausea, vomiting, right upper quadrant pain or tenderness, fever, or rash
- e. ALT or AST $\geq 5 \times$ ULN but $< 8 \times$ ULN and cannot be monitored at least weekly for ≥ 2 week

Hy's Law, defined as $\geq 3 \times$ ULN ALT or AST **with coexisting** $\geq 2 \times$ ULN total bilirubin with no alternative explanation for the biochemical abnormality other than IMP (for example elevated ALP indicating cholestasis, viral hepatitis, other medication) must always be reported without delay as an AESI, and, if applicable, also as an SAE.

All potential AESIs will be medically evaluated during the study, before the database lock and unblinding, by the sponsor to identify events which could possibly be AESIs.

A list of PTs for AESIs will be provided for identification and AESIs will be flagged in the database.

The following summary and listing will be provided.

- A summary of the number and percentage of patients reporting an AESIs by SOC and PT.
- Listing of AESIs

4.11.3 Deaths, Serious Adverse Events, and Other Significant Adverse Events

The following summaries will be provided by treatment group and overall.

- A summary of the number and percentage of deaths (including SAEs with fatal outcome and deaths as PT),
- A summary of the number and percentage of patients reporting a serious TEAE, by SOC and PT,
- A summary of the number and percentage of patients with TEAEs leading to discontinuation of study treatment, by SOC and PT.

The following listings will be provided:

- A listing of all deaths that occurred during the study,
- A listing of all SAEs,
- A listing of all AEs leading to discontinuation of study treatment.

4.11.4 Clinical Laboratory Evaluation

The following laboratory parameters of hematology, blood chemistry, coagulation and urinalysis will be assessed at screening, Visit 3 (Day 7), Visit 5 (Days 28) and Visit 9 (EOS):

Hematology: Hematocrit, Hemoglobin (Hb), Platelet count, Red blood cell (RBC) count and White blood cell (WBC) count with differential count.

Blood chemistry: Alanine aminotransferase (ALAT), Alkaline phosphatase (ALP), Albumin, Aspartate aminotransferase (ASAT), Bilirubin (total and conjugated), Calcium, Chloride, Creatinine, Gamma-glutamyl transferase (GGT), Magnesium, Phosphorous, Potassium, Sodium, Urea nitrogen, Uric acid and Gastrin.

Coagulation: International Normalized Ratio.

Urinalysis (dip stick): Glucose, Hemoglobin/erythrocytes, Nitrite, Protein, Specific gravity, pH and Ketones.

Urine Drug Screen: Amphetamine, Barbiturate, Cannabinoid, Cocaïne, Benzodiazepine and Opiate.

Serum Gastrin

Laboratory test results for hematology, chemistry, and coagulation parameters will be classified as normal or abnormal (high or low) according to the applicable laboratory's normal ranges.

For by-visit summaries, the last non-missing assessment (including repeat assessments) recorded at each visit will be summarized. Baseline is defined as the last assessment prior to study drug intake and will be the screening assessment.

The following summaries will be based on the Safety Analysis Set.

Summaries for actual values and change from baseline will be presented by treatment group and assessment day for each study site separately (due to assays performed locally). Summaries for categorical values of normality/abnormality will be presented by treatment group and assessment day.

- Hematology and coagulation: laboratory test value and change from baseline by visit
- Hematology and coagulation: laboratory test value and change from baseline by visit in patients with LA grade A/B
- Hematology and coagulation: laboratory test value and change from baseline by visit in patients with LA grade C/D
- Hematology and coagulation: number and percentage of patients experiencing low, normal or high laboratory test result
- Hematology and coagulation: number and percentage of patients experiencing low, normal or high laboratory test result in patients with LA grade A/B
- Hematology and coagulation: number and percentage of patients experiencing low, normal or high laboratory test result in patients with LA grade C/D
- Chemistry: laboratory test value and change from baseline by visit
- Chemistry: laboratory test value and change from baseline by visit in patients with LA grade A/B
- Chemistry: laboratory test value and change from baseline by visit in patients with LA grade C/D
- Chemistry: number and percentage of patients experiencing low, normal or high laboratory test result
- Chemistry: number and percentage of patients experiencing low, normal or high laboratory test result in patients with LA grade A/B
- Chemistry: number and percentage of patients experiencing low, normal or high laboratory test result in patients with LA grade C/D
- Urinalysis: laboratory test category (normal, abnormal not clinically significant or abnormal clinically significant) and toxicity grade by visit
- Urinalysis: laboratory test category (normal, abnormal not clinically significant or abnormal clinically significant) and toxicity grade by visit in patients with LA grade A/B
- Urinalysis: laboratory test category (normal, abnormal not clinically significant or abnormal clinically significant) and toxicity grade by visit in patients with LA grade C/D
- Serum Gastrin: laboratory test value and change from baseline by visit

- Serum Gastrin: laboratory test value and change from baseline by visit in patients with LA grade A/B
- Serum Gastrin: laboratory test value and change from baseline by visit in patients with LA grade C/D

Laboratory values (hematology, chemistry, coagulation and urinalysis) will be listed by patient and study time point including changes from baseline (with the exception of urinalysis).

All values outside the clinical reference ranges will be flagged in the data listings. The abnormal values will be flagged with 'L' for values below the lower limit of the clinical reference range and 'H' for values above the upper limit of the clinical reference range and included in the listings.

The following listings of laboratory parameters will be provided:

- Hematology and coagulation parameters
- Chemistry parameters
- Urinalysis

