2.3.1 Summary of Risk Management

Visits at the clinic/investigational site may be prolonged in case the Investigator finds it medically warranted for safety reasons. In cases of accidental overdose, standard supportive measures should be adopted as required. For further information regarding overdosing, refer to Section 8.5.

Each patient will be provided with a Patient Identification Card with information about the patient participation in a study, see Section 10.1.4.

The Principal Investigator at the research clinic/investigational site will ascertain that adequate facilities and procedures are available to handle emergency situations.

Besides the risks related to the IMP as described above, there may also be risks related to the repeated endoscopy after 4 weeks. Other medical devices, e.g., indwelling venous catheters, are used in routine medical care and the risk associated with their use is considered low and ethically justifiable. Study-specific evaluations and sampling procedures, like blood-pressure measurements using a blood pressure cuff and blood sampling, may cause transient discomfort but the risk is deemed to be low and ethically justifiable.

Linaprazan is the acid inhibitory metabolite of the X842 molecule. Linaprazan has been extensively studied and in a small number of patients increased LFTs were observed [3, 4] and careful evaluation concluded that the high C_{max} of linaprazan was the main reason for the LFT increase. The C_{max} of the metabolite linaprazan following administration of its prodrug X842 is reduced with about 75% and thereby minimizing the risk for hepatotoxicity. Overall, the combined safety data from the pre-clinical and clinical studies have not revealed any safety

issues that would outweigh the expected benefits of the study. While keeping the above-mentioned risk factors at a minimum level in order to not expose the patients participating in the study for risks that would not be ethically justifiable it is concluded that the planned study assessments are considered sufficient to meet the scientific and medical objectives of the study. It is therefore concluded that the potential benefits from the study will outweigh the potential risks for the treated patients.

More detailed information about the known and expected benefits and risks and reasonably expected ADRs of X842 is found in the IB.

3 Objectives and Endpoints

Objectives	Endpoints
Primary	

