Every liver laboratory trigger or liver event as defined in Table 2 should be followed up by the Investigator or designated personnel at the trial site as summarized below (please also refer to General withdrawal criteria, Section 7.1).

A. Liver laboratory trigger:

- Repeating the LFT within the next week to confirm elevation. The repeat assessment can be done as an unscheduled study visit or at a local laboratory. In this case, local laboratory normal ranges should be recorded, and the results should be made available to the trial investigator immediately, and the data recorded on the CRF.
- If the elevation is confirmed, close observation of the patient will be initiated, including consideration of treatment interruption if deemed appropriate.

B. Liver event:

- Repeating the LFT as soon as possible to confirm elevation as appropriate
- Monitoring of liver chemistry values at least twice per week until values normalize, stabilize, or return to within baseline value
- Discontinuation of the investigational drug if appropriate
- Hospitalization of the patient if appropriate
- A causality assessment of the liver event via exclusion of alternative causes (e.g., disease, co-medications)
- An investigation of the liver event which needs to be followed until resolution.

These investigations can include serology tests, imaging and pathology assessments, hepatologist's consultancy, based on investigator's discretion. All follow-up information, and the procedures performed should be recorded on appropriate CRF pages, including the liver event overview CRF pages.

Table 2 Liver Event and Laboratory Trigger Definitions

	Definition/ threshold
A. LIVER LABORATORY TRIGGERS	ALT or AST > 3 × ULN, but ALT and AST ≤ 5 × ULN TBL > 1.5 × ULN, but TBL ≤ 2 × ULN
B. LIVER EVENTS	
Laboratory events (any of the listed criteria)	ALT or AST > 5 × ULN ALP > 5 × ULN TBL > 2 × ULN (in the absence of known Gilbert syndrome) Potential Hy's Law cases (defined as ALT or AST > 3 × ULN and TBL > 2 × ULN [mainly conjugated fraction] without notable increase in ALP to > 2 × ULN)
Adverse events (any of the listed criteria)	Any clinical event of jaundice (or equivalent term) ALT or AST > 3 × ULN accompanied by (general) malaise, fatigue, abdominal pain, nausea, or vomiting, or rash with eosinophilia Any adverse event potentially indicative of a liver toxicity *

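### Last-value laboratory tables, with no worst-value or multiple-of-ULN table, can hide the size of a transient liver elevation, and sometimes the elevation itself, by dose group

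*SAP*

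**What the plan says.** SAP 4.11.4 (Clinical Laboratory Evaluation) sets the selection rule: "For by-visit summaries, the last non-missing assessment (including repeat assessments) recorded at each visit will be summarized". Actual values and changes from baseline are shown by arm and assessment day, but for each site separately. The categorical tables follow the same visit structure: "Summaries for categorical values of normality/abnormality will be presented by treatment group and assessment day". For chemistry the categorical output is "Chemistry: number and percentage of patients experiencing low, normal or high laboratory test result", repeated for LA grades A/B and C/D. Protocol 9.4.8 explains that pooling across sites is possible because results are classified into categories.

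Protocol 8.4.1.3 governs liver re-testing. After a liver laboratory trigger (Table 2) the site's first action is "Repeating the LFT within the next week to confirm elevation", and "The repeat assessment can be done as an unscheduled study visit or at a local laboratory". After a liver event it is "Repeating the LFT as soon as possible to confirm elevation as appropriate", followed by "Monitoring of liver chemistry values at least twice per week until values normalize, stabilize, or return to within baseline value". Local results and their normal ranges are to be recorded on the CRF.

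The SAP amendment leaves the original SAP in force unless it says otherwise. In the text that is shown, it does not change the laboratory tables.

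**The concern.** Repeat liver tests in this trial are not a random second look. They exist because the first value was high, and after a liver event they continue until values settle. A rule that takes the last value at a visit, repeats included, can therefore replace the value that prompted the re-test with one taken after recovery.

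Protocol 2.3.1 gives the reason to look closely. With linaprazan, the active metabolite, "in a small number of patients increased LFTs were observed", and the protocol attributes this to high Cmax. Protocol 2.2 names safety data as one of three inputs to the Phase 3 dose choice, with healing and PK. The laboratory tables by arm are where a reader would look for a dose-related rise in liver enzymes. As planned, they may omit a transient rise, and they never show how large any rise was.

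**Working it through.** The plan states no figure to reproduce. The check sets the selection rule against the re-test procedure and then against every table that could show the elevation.

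**1. What a trigger means.** Exclusion criterion 11 bars screening ALT or AST above 1.5 × ULN. An on-treatment value above 3 × ULN is therefore more than 3 / 1.5 = 2 times the highest value allowed at entry.

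**2. How many scheduled looks there are.** The Schedule of Assessments has safety laboratory tests at screening, Visit 3 (Day 7), Visit 5 (Day 28) and Visit 9. Only Visits 3 and 5 are post-baseline looks in the double-blind phase. A repeat prompted by Visit 5 can fall up to a week later, when the patient is on open-label lansoprazole.

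**3. Which elevations the AESI tables count.** Table 2 of Protocol 8.4.1.3 (its two trigger lines read as alternatives) set against the AESI list in the same section and in SAP 4.11.2:

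| Elevation | Table 2 status | AESI? |
|---|---|---|
| ALT/AST above 3 and below 5 × ULN, isolated, no symptoms | laboratory trigger | no |
| ALT/AST above 5 and below 8 × ULN, under 2 weeks, monitored weekly, isolated, no symptoms | liver event | no |
| Total bilirubin above 2 × ULN alone | liver event | no |
| ALP above 5 × ULN alone | liver event | no |
| ALT/AST at or above 8 × ULN | liver event | yes |

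The first four rows reach an AE table only if the value is reported as an AE, which for a laboratory value turns on clinical significance. The SAP plans no count of Table 2 triggers or liver events. SAP 4.11.2 identifies AESIs through sponsor review and a list of preferred terms; it states no derivation from the laboratory data.

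**4. What the laboratory tables show.** Four traces for one patient, with assumed values:

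- A. Day 7 ALT 4.0 × ULN, repeat 0.9 × ULN filed under Visit 3. The last value is 0.9, so the category is normal and the elevation is gone from the table.
- B. Day 7 ALT 4.0 × ULN, repeat 1.5 × ULN filed under Visit 3. The category stays high, but the 4.0 is lost from the site-level value table.
- C. Day 7 ALT 4.0 × ULN, repeat 0.9 × ULN filed as an unscheduled visit. The 4.0 stays in the Day 7 row and nothing is overwritten. In the pooled table it shares a cell with 1.1 × ULN.
- D. As C, but the unscheduled repeat is 6.0 × ULN. Day 7 shows high, and the 6.0 enters no by-visit table.

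The SAP does not say whether unscheduled or local repeats are assigned to a scheduled visit, so the documents do not determine which trace applies.

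**5. Other outputs.** SAP 4.2 allows shift tables where appropriate, but 4.11.4 lists none. Toxicity grade is planned for urinalysis and not for chemistry. Listings keep the flagged out-of-range values by patient.

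**The case against.** The strongest reply has four parts.

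- The rule covers repeats recorded at a visit, and the protocol lets the re-test be an unscheduled visit or a local test. On that route the first high value stays in its row. This stands: overwriting is possible, not certain.
- The AE outputs do not use the last-value rule. TEAEs are tabulated by arm, SOC/PT and severity; AESIs are counted by arm, with a SOC/PT table. This stands for everything that meets an AESI criterion or is reported as an AE. It does not cover the first four rows of the table above.
- A repeat may be higher than the first value, in which case the last-value rule raises the entry. This also stands.
- Protocol 2.3.1 expects linaprazan Cmax after X842 to be about 75% lower, and choosing first or last values for descriptive means is a convention. Both are fair, but a lower expected risk is something the tables should be able to check by dose.

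A reader might infer several stronger claims that the documents do not support:

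- *Severe liver cases disappear from dose-group reporting.* A value at or above 8 × ULN is an AESI.
- *The stopping rules are blinded to liver signals.* Protocol 10.1.9 rests its liver-related criteria on AESI and Hy's Law counts, not on these tables.
- *The tables are biased downwards, most in the high-dose arms.* This needs both a dose effect and a filing practice that the documents do not state.
- *Arm means for liver enzymes are distorted.* Value summaries are by site, so no pooled arm mean is planned.
- *Vital signs share the problem.* SAP 4.11.5 has the same rule, but the protocol requires no re-test after an abnormal vital sign, so the selection mechanism is absent.

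**Conclusion.** The point holds in a limited form. A transient liver elevation that is neither an AESI nor reported as an AE can read normal in the pooled laboratory table, provided its repeat is at or below ULN and is filed under the same scheduled visit. If the repeat is filed as unscheduled, the first value survives but any higher later peak does not reach a by-visit table. Under either filing practice, no laboratory table pooled across sites shows by dose how large an elevation was.

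The number of patients affected cannot be derived. It depends on how many have such an elevation, and on what share of those have a repeat at or below ULN filed under the same visit. The documents give neither. At a share of 0 no high flag is lost; at a share of 1 all of them are. The loss of magnitude does not depend on that share.

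This is a reporting gap in a secondary safety objective. It does not touch the primary healing analysis and does not suggest that serious liver events go uncounted. It is worth correcting because the correction is cheap and the tables feed the dose choice.

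**What to change.** In SAP 4.11.4:

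- Use the scheduled (first) value for by-visit liver chemistry summaries, and state how repeat, unscheduled and local results are assigned to visits.
- Add a by-arm table of each patient's worst post-baseline ALT, AST, ALP and total bilirubin, using all scheduled, repeat, unscheduled and local values, each against its own laboratory's ULN.
- Show the double-blind phase separately from open-label lansoprazole, and state how repeats prompted by a Visit 5 value but drawn after the switch are assigned.
- Categorise by multiples the protocol already uses: ALT/AST 3, 5 and 8; total bilirubin 1.5 and 2; ALP 5; ALT/AST 3 combined with bilirubin 2.

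Before programming, the sponsor must reconcile the cut-points. Protocol 7.1 and Table 2 use strict inequalities, while the AESI list in 8.4.1.3 uses at-or-above. Protocol 7.1 and the AESI list also word the two-week duration differently. Which wording is right is for the sponsor to settle.

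The cost is SAP wording and a few extra tables from data the protocol already collects, including local ranges on the CRF. No patient or site procedure changes.

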1. Including smoking (current status), alcohol consumption, and intake of drug of abuse.
2. Height only at screening
3. Human immunodeficiency virus (HIV), hepatitis B surface antigen (HBsAg), hepatitis B core antigen (anti-HBcAg), antibody to hepatitis C virus (anti-HCV) testing at central and/or local laboratory. Patient should discontinue the study if result from central laboratory is positive.
4. Systolic and diastolic blood pressure (BP) [mmHg], heart rate [beats per minute], body temperature and respiratory rate [per minute].
5. Hematology, blood chemistry, coagulation (central laboratory), urinalysis (at site). Serum gastrin at screening and at Visit 5 (central laboratory).
6. *H. pylori* will be analyzed in central laboratory from serum and the result will not be needed for randomization.
7. Women of childbearing potential only. Serum pregnancy test at central laboratory at screening and urine pregnancy test at clinic/investigational site prior to the dose administration at Visit 5, and at End of Study / Early Termination.
8. PK measured in all patients just before the first and the second dose on the day of the visit. At all PK sampling occasions, the time since latest study drug administration must be noted in the case report form (CRF). Pharmacokinetic samples will be collected 12 hours after the previous study drug dose administration or as close to this timepoint as possible, however, still pre-dose.
9. QOLRAD assessment must be done pre-dose. QOLRAD will be completed by patients during site visits at Visit 2, 3, 4, 5 and 9.
10. Patients will be trained on how to complete the symptoms diary during Visit 2 and the actual diary will be provided at Visit 2.

11. At each visit, Investigator should assess the severity of patients' heartburn, regurgitation and dysphagia in the 7 days prior to the visit. The assessment will include both the severity grade and the frequency of symptoms. Symptoms are scored as follows: none (no complaints), mild (aware of symptom, but easily tolerated), moderate (discomforting symptom, sufficient to cause interference with normal daily activities and/or sleep), severe (incapacitating symptom, with inability to perform normal daily activities and/or sleep)
12. Collection of AEs will start directly after the informed consent form (ICF) has been signed. During the screening period, only AEs related to study procedure will be reported.
13. For definitions of prior and concomitant medication, see Section 8.1.6.

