- Serum ALT or AST $> 1.5 \times$ the upper limit of normal (ULN) for the central laboratory conducting the test
- Serum Total Bilirubin $> 1.5 \times$ ULN for the central laboratory conducting the test
- Serum Creatinine $> 1.5 \times$ ULN for the central laboratory conducting the test
- Estimated glomerular filtration rate ≤ 59 mL/min (calculated using the Modification of Diet in Renal Disease equation)

12. History of a positive result for human immunodeficiency virus (HIV), Hepatitis B surface antigen (HBsAg), antibody to Hepatitis B core antigen (anti-HBcAg), or antibody to Hepatitis C virus (anti-HCV) or presence of these findings on screening

Note: Patients with positive anti-HBcAg along with negative HBsAg at screening will not be excluded IF they have a positive local anti-HBs test results not older than 6 months and active HBV infection has been ruled out by the Investigator.

13. After 10 min supine rest at the time of screening, any vital signs values outside the following ranges:
 - Systolic blood pressure (BP) > 160 mmHg or < 90 mmHg
 - Diastolic BP > 100 mmHg or < 60 mmHg
 - Heart rate < 40 or > 95 beats per min
14. History of long QTc syndrome (e.g., QTc \geq 450 ms for males and \geq 470 ms for females)
15. Cardiac arrhythmias or any clinically significant abnormalities in the resting 12-lead ECG at the time of screening, as judged by the Investigator
16. History of severe allergy/hypersensitivity or ongoing allergy/hypersensitivity, as judged by the Investigator, or history of hypersensitivity to drugs with a similar chemical structure or class to X842 or lansoprazole
17. Administration of another new chemical entity (defined as a compound which has not been approved for marketing) or has participated in any other clinical study that included drug treatment with less than one month between administration of last dose and first dose of IMP in this study.
18. Positive screen for drugs of abuse at screening (for the list of drugs for testing please refer to the laboratory manual).
19. Current or history of alcohol, drug abuse and/or use of anabolic steroids within 2 years prior to screening
20. Women who are pregnant or breast feeding.
21. Patient is an employee of the Investigator or study site, with direct involvement in the proposed study or other studies under the direction of that Investigator or study site, as well as family members of the employees or the Investigator.

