9.4.8 Safety Analyses

All safety analyses will be performed on the Safety Set.

Endpoint	Statistical Analysis Methods
Evaluate the safety and tolerability of the four dose levels of X842 and lansoprazole, where lansoprazole will serve as the active comparator.	Physical examination, weight, BMI, vital signs, electrocardiogram (ECG) recordings, safety laboratory measurements (hematology/clinical chemistry/urinalysis), adverse event (AE), treatment emergent adverse event (TEAE), adverse event of special interest (AESI), serious adverse event (SAE) reporting, concomitant medication(s).
Weight and BMI	Weight and BMI will be presented by patient and summarized by treatment using descriptive statistics along with absolute and percent change.
Vital signs	For BP and heart rate, descriptive statistics of actual values and change from screening will be used for summaries by treatment group and assessment day. Categorically classified (Normal/Abnormal) results will also be summarized.
12-lead ECG	ECG variables will be summarized according to actual values and change from screening using summary statistics and will be presented by treatment group and assessment visit. Categorically classified (Normal/Abnormal) results will also be summarized.
Safety laboratory analyses	All hematology, clinical chemistry and coagulation laboratory tests will be summarized using descriptive statistics for actual values and change from screening and presented by treatment group and assessment day for each study site separately (due to assays performed locally). Additionally, the local laboratory normal ranges will be used to classify the results as: High, Normal or Low and categorical summaries will be presented overall according to treatment group and assessment visit. Pooling across all sites is possible due to the categorical classification.
Adverse events	All AEs will be summarized according to TEAE or baseline symptom following classification of the verbatim terms according to the MedDRA dictionary. The number and percentage of patients for all classified events will be presented according to System organ class (SOC) and Preferred term (PT) by treatment group and overall. Separate summaries will be presented for all AEs by event frequency of occurrence and also for all AEs according to seriousness, severity and relationship. Separate summaries will be presented for AEs of Special Interest

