Assessment/Study day	Day -7 ¹⁴ to Day 0	Day 0	Day 7 ±2 days	Day 14 ±3 days	Day 28 -2/+5 days	Day 35 ±3 days	Day 42 ±3 days	Day 49 ±3 days	Day 56 ±3 days
Assessment/Study week		Randomization	Week 1	Week 2	Week 4	Week 5	Week 6	Week 7	Week 8
	Screening Period		Blinded Treatment Phase				Open-Label Phase		
Symptom assessment by Investigator ¹¹	X	X	X	X	X	X	X	X	X
AE reporting ¹²	X	X	X	X	X	X	X	X	X
Prior/concomitant medications ¹³	X	X	X	X	X	X	X	X	X

Abbreviations: AE, adverse event; ECG, electrocardiogram; ICF, informed consent form; LA, Los Angeles; PK, pharmacokinetic.

1. Including smoking (current status), alcohol consumption, and intake of drug of abuse.
2. Height only at screening
3. Human immunodeficiency virus (HIV), hepatitis B surface antigen (HBsAg), hepatitis B core antigen (anti-HBcAg), antibody to hepatitis C virus (anti-HCV) testing at central and/or local laboratory. Patient should discontinue the study if result from central laboratory is positive.
4. Systolic and diastolic blood pressure (BP) [mmHg], heart rate [beats per minute], body temperature and respiratory rate [per minute].
5. Hematology, blood chemistry, coagulation (central laboratory), urinalysis (at site). Serum gastrin at screening and at Visit 5 (central laboratory).
6. *H. pylori* will be analyzed in central laboratory from serum and the result will not be needed for randomization.
7. Women of childbearing potential only. Serum pregnancy test at central laboratory at screening and urine pregnancy test at clinic/investigational site prior to the dose administration at Visit 5, and at End of Study / Early Termination.

8. PK measured in all patients just before the first and the second dose on the day of the visit. At all PK sampling occasions, the time since latest study drug administration must be noted in the case report form (CRF). Pharmacokinetic samples will be collected 12 hours after the previous study drug dose administration or as close to this timepoint as possible, however, still pre-dose.
9. QOLRAD assessment must be done pre-dose. QOLRAD will be completed by patients during site visits at Visit 2, 3, 4, 5 and 9.
10. Patients will be trained on how to complete the symptoms diary during Visit 2 and the actual diary will be provided at Visit 2.

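### Laboratory values and changes are to be tabulated site by site because assays are said to be local, but both Schedules of Assessments send the blood tests to a central laboratory, so no trial-wide mean change by dose is planned

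*SAP*

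**What the plan says.** SAP 4.11.4 states that summaries of actual values and change from baseline are given by treatment group and assessment day "for each study site separately (due to assays performed locally"). That sentence introduces the whole list of value-and-change tables: hematology and coagulation, chemistry, and serum gastrin, each repeated for LA grade A/B and C/D. Only the normal/abnormal tables are described without a site split.

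Protocol 9.4.8 has the same rule: "presented by treatment group and assessment day for each study site separately (due to assays performed locally"). It adds that "the local laboratory normal ranges will be used to classify the results" as high, normal or low, and that "Pooling across all sites is possible due to the categorical classification".

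Footnote 5 of Protocol 1.3 says otherwise about where the tests are run: "Hematology, blood chemistry, coagulation (central laboratory), urinalysis (at site"). SAP 6.1 repeats the footnote, including "Serum gastrin at screening and at Visit 5 (central laboratory"). Exclusion criterion 11 in Protocol 5.2 sets its liver, bilirubin and creatinine limits by the ULN "for the central laboratory conducting the test".

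Local liver testing appears in Protocol 8.4.1.3 as follow-up. After a liver trigger the repeat may be done locally, in which case "local laboratory normal ranges should be recorded". Where local tests are done for speed, a parallel central sample is requested if possible.

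**The concern.** The only reason given for splitting continuous laboratory results by site is that the assays are local, and the procedures in the same documents say they are not. Followed literally, the plan yields many small arm-by-site tables and no all-site mean change by dose.

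This matters here for two reasons. Protocol 2.3.1 reports raised liver tests in a few patients given linaprazan, the active metabolite. Protocol 2.2 makes the safety data at each dose part of the basis for choosing the Phase 3 dose. The pooled low/normal/high counts cannot separate a value just above the ULN from a multiple of it, and they do not show how much gastrin changes with dose.

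Two related gaps follow. SAP 4.11.4 summarises the last non-missing result at each visit, repeats included, without saying whether a locally run repeat replaces a central value. SAP 4.11.2 identifies AESIs by a preferred-term list and sponsor medical review; it specifies no programmed check of laboratory results against the AESI thresholds, so a qualifying value could be overlooked.

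**Working it through.** **Comparing the passages**

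| Item | Statistical text (Protocol 9.4.8, SAP 4.11.4) | Procedures (footnote 5, both documents) |
|---|---|---|
| Hematology, chemistry, coagulation | Assays local; values and changes by site | Central laboratory |
| Gastrin | Under the same by-site sentence in the SAP | Central laboratory |
| Urinalysis | Categories only | At site |

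The urine dipstick, the one routine safety test run at site, is reported only in categories. The tests the by-site rule does cover are all central according to footnote 5. No readable sentence in the protocol, the SAP or the SAP amendment adds an all-site table of values and changes. Section 4.5.3 of the amendment only places the safety analyses on the Safety Analysis Set. Parts of the amendment are blacked out.

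**How thin the site tables would be**

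The plan states no figure on this point, so there is nothing to reproduce. What follows only shows scale.

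Inputs: about 240 patients, 48 per arm, 5 arms (Protocol 1.1); at most 48 patients per site (Protocol 4.1); about 50% in each LA stratum (Protocol 6.3.1).

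Assumptions: equal site sizes and no missing values. The number of sites is not given; 10 is illustrative.

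- Minimum number of sites: 240 / 48 = 5.
- Patients per arm per site: 48 / 5 = 9.6 at 5 sites; 48 / 10 = 4.8 at 10 sites.
- Patients per arm per site in one LA table at 5 sites: 9.6 × 0.5 = 4.8. Pooled over sites: 48 × 0.5 = 24.

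Half-width of a 95% interval for a mean change, in SD units, is t(0.975, n − 1) / √n, with non-integer degrees of freedom allowed:

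| Cell | n | Calculation | Half-width (SD) |
|---|---|---|---|
| Arm, all sites | 48 | 2.012 / 6.928 | 0.29 |
| Arm, one LA stratum, all sites | 24 | 2.069 / 4.899 | 0.42 |
| Arm at one of 5 sites | 9.6 | 2.278 / 3.098 | 0.74 |
| Arm at one of 10 sites, or arm and LA stratum at one of 5 sites | 4.8 | 2.835 / 2.191 | 1.29 |

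Against the pooled arm, the site cells are 0.735 / 0.290 = 2.5 times wider at 5 sites and 1.294 / 0.290 = 4.5 times wider at 10. For one LA stratum at 5 sites the ratio is 1.294 / 0.422 = 3.1.

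The SAP plans no interval for laboratory values, so the half-width is only a measure of how readable the cells would be.

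**The case against.** **The output titles do not say by site.** The SAP labels its healing output by center when it wants that split, and the laboratory titles carry no such label, so a programmer might pool. That is possible, but the introductory sentence governs the list and an unlabelled title does not override it. The ambiguity is itself a reason to correct the text.

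**The SAP has partly moved on.** It classifies results by the applicable laboratory's ranges, which suits a central laboratory, and it omits the protocol's remark on pooling. This is true, but the by-site clause and its reason remain in the SAP.

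**Liver signals are outliers, and other outputs catch them.** Raised liver tests in a few patients are not best seen in a mean. There is also 24-hour AESI reporting, laboratory alerts, blinded sponsor review, flagged listings, and adverse event tables by severity and treatment group. These do catch individual cases, and liver findings would not go wholly unseen by dose. They do not summarise laboratory change by dose.

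**Local testing is broader than liver repeats.** Viral serology, anti-HBs and urine tests may also be local, and repeats outside a visit may never enter the by-visit means. None of the first three falls in the value-and-change tables. Whether local repeats enter is what the SAP leaves unsaid.

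**The size rests on assumptions.** This stands: the site count is unknown. The equal LA split is a randomization target, whereas SAP 4.10.2 uses central reading for reporting. Patients reread as grade 0 belong to neither LA table, which lowers the average across the two; movement between grades enlarges one table at the other's expense.

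**The table of ULN multiples goes beyond the correction.** It does, and it is offered only as an addition.

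**Conclusion.** The concern holds. Protocol 9.4.8 and SAP 4.11.4 rest the site split on a premise that footnote 5 in both documents contradicts. As written, the plan contains no all-site mean change by dose for ALT, AST, bilirubin or gastrin.

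The contradiction depends on no assumption. The scale does: with equal sites and complete data, an arm-by-site mean is about 2.5 times less precise than the pooled arm mean at the minimum of 5 sites, and about 4.5 times at an assumed 10. Collected data and patient listings are unaffected, and individual liver cases have other safeguards. What is lost is the by-dose summary of laboratory change, in a trial whose safety data by dose feed the Phase 3 choice. It should be corrected.

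**What to change.** Reconcile Protocol 9.4.8 and SAP 4.11.4 with footnote 5.

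1. Remove the by-site split and its stated reason from both documents. In Protocol 9.4.8 also correct the reference to local normal ranges and the sentence that makes pooling depend on categories.
2. Suggested text: *Centrally analysed hematology, chemistry, coagulation and gastrin results, and their changes from baseline, will be summarised by treatment group and visit with all sites pooled. Locally analysed repeats will be left out of these summaries; they will be listed and compared with their own recorded ULN for threshold classification.* State that this changes the SAP's rule on including repeats.
3. As a cheap addition, derive by program a table, by treatment group, of patients whose ALT/AST, bilirubin and INR results meet the ULN-multiple and INR thresholds already in the AESI definitions. Reconcile it with the reported AESIs, keeping the preferred-term list and blinded sponsor review. AESI criteria (d) and (e) still need symptom or monitoring information.
4. If some blood tests were in fact run locally, correct footnote 5 instead and name them.

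The cost is a wording change in two documents and one derived table. The per-site tables fall away and no new data are collected.
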